6.4 Study Drug Compliance

Study drug will be dispensed under the instructions of the investigator or designee and under medical supervision. The date and time of dose administered will be recorded in the source documents and in the CRF. The dose of study drug and study participant identification will be confirmed at the time of dosing by a member of the study site staff other than the person administering the study drug. The investigator may terminate study drug administration at his/her discretion.

6.5 Continued Access to Study Drug after the End of the Study

Not applicable in this trial.

6.6 Participant Infusion Stopping Criteria

Because RNS60 chemically contains only sodium chloride and oxygen, and based on the nonclinical and clinical safety information, the sponsor does not recommend specific treatment for an overdose. However, because a saline infusion of up to 130 mL/h for 48h could present a volume challenge the investigator should:

- 1) Contact the PI and sponsor in case of any signs of possible fluid overload, including worsening dyspnea, hypoxia, or cardiac function which do not resolve with treatment.
- 2) Closely monitor the participant for any AEs/SAEs and electrocardiogram (ECG), CXR, laboratory abnormalities for at least 1 day. (See [Section 8.1.2 Clinical Safety Laboratory Assessments](#) for additional infusion stopping criteria related to ECG values).
- 3) Document the quantity (infusion duration) in the CRF.

6.7 Concomitant Therapy

There are no restricted medications in this trial.

Any medication or vaccines (including over the counter or prescription medicines) that the participant is receiving at the time of enrollment or receives up to Day 90 must be recorded along with:

- Dates of administration including start and end dates, medications that were ongoing at the last contact will be updated with a stop date or confirmed as ongoing,
- Indication for use.

6.8 Rescue Medicine/Treatment

6.8.1 Early Study Drug Cessation

The intervention is 0.5 mL/kg/h RNS60 (up to a maximum of 65 mL/h) and 1 mL/kg/h RNS60 (up to a maximum of 130 mL/h) intravenous infusion using an infusion pump, starting after randomization to a participant undergoing endovascular mechanical thrombolysis/thrombectomy. It is expected that infusion will begin prior to the completion of the procedure (defined as the time of arterial access closure) and complete 48h after the infusion is initiated.

The infusion may be stopped if the treating investigator believes the volume of infusion can no longer be tolerated due to volume overload (worsening dyspnea, hypoxia, or cardiac function). As such, the investigator may terminate drug administration at his/her discretion.

6.9 Endovascular Intervention and Stroke Care

EVT should be conducted as per the local protocol and in compliance with the current treatment guidelines such as those published by the American Heart Association (AHA)¹⁹⁻²¹. All participants are expected to be admitted to the hospital as part of routine standard of care. All participants are expected to receive expert stroke unit care and then rehabilitation according to their clinical need throughout the full 90 days.

7 DISCONTINUATION of STUDY DRUG and PARTICIPANT DISCONTINUATION / WITHDRAWAL

7.1 Discontinuation of Study Drug

In rare instances, it may be necessary for a participant to permanently discontinue (definitive discontinuation) study drug. If study drug administration is discontinued, the participant will remain in the trial and be evaluated to Day 90.

7.2 Participant Discontinuation/Withdrawal from the Trial

Participation in this clinical trial may be discontinued for any of the following reasons:

- Administrative reasons (uncooperative, noncompliant, etc.)
- Participant's decision not to participate any further
- If it is in the participant's best interest, per the qualified/principal or sub-investigator

If the participant or legally authorized representative (LAR) withdraws consent, participant data will be included in the analysis up to the date of the consent withdrawal and this withdrawal of consent will be documented in the CRF.

If the LAR has originally provided consent and the participant subsequently declines consent, this will be deemed to be a withdrawal of consent. The investigator and sponsor would continue to have access to data that have already been collected.

A participant may not withdraw use of his or her data that have already been collected. This is in alignment with the FDA guidance document "Data Retention When Participants Withdraw from FDA-Regulated Clinical Trials", which is based on the importance of avoiding selection biases that could compromise the analysis of the overall trial.

Otherwise, all randomized participants will continue to be followed according to protocol requirements and follow-up data will be included in the analysis. Criteria for removal of participants will be recorded and reported.

7.3 Lost to Follow up

A participant will be considered lost to follow-up if he/she repeatedly fails to return for scheduled visits/contacts and is unable to be contacted by the study site. The following actions must be taken if a participant fails to return to the clinic or if they cannot be contacted by phone for a required study visit:

- The site must attempt to contact the participant and reschedule the missed visit/contact as soon as possible and counsel the participant on the importance of maintaining the assigned visit schedule and ascertain whether or not the participant wishes to and/or should continue in the trial.

- Before a participant is deemed lost to follow up, the investigator or designee must make every effort to regain contact with the participant (at a minimum 3 telephone calls/contacts). These contact attempts should be documented in the participant's study record.
- Should the participant and/or LAR continue to be unreachable, he/she will be considered to have withdrawn from the trial. Every effort will be made to collect functional assessment and/or mortality data or any other data from the LAR if the participant is unreachable.
- Site personnel will attempt to collect the vital status of the participant within legal and ethical boundaries for all participants randomized, including those who did not get study intervention. Public sources may be searched for vital status information. If vital status is determined as deceased, this will be documented, and the participant will not be considered lost to follow-up. Sponsor personnel will not be involved in any attempts to collect vital status information.

8 STUDY ASSESSMENTS and PROCEDURES

Study procedures and their timing are summarized in [Table 1-1: Schedule of Activities](#). Adherence to the trial design requirements is essential and required for study conduct.

Procedures conducted as part of the participant's routine clinical management (e.g., blood count) and obtained before signing of the ICF may be utilized for baseline purposes provided the procedures met the protocol-specified criteria and were performed within the time frame defined in [Table 1-1: Schedule of Activities](#).

8.1 Safety and Efficacy Assessments

Planned time points for all safety and efficacy assessments are provided in [Table 1-1: Schedule of Activities](#). Further definition/description of those assessments are provided here:

8.1.1 Vital Signs

Blood pressure and heart rate will be taken at baseline (pre-dose) and per routine (every 8-12 hours) until completion of the infusion at 48h. Results taken from standard of care assessment/timepoints may be used. Temperature will be taken at baseline (if available per standard of care). Clinically significant findings post-dose will be reported as AEs.

8.1.2 Clinical Safety Laboratory Assessments

Blood work will be done at baseline (within 4 hours of admission) and at Day 2 (48h +/- 4 hours), and include: complete blood count (hemoglobin, platelets and hematocrit), full metabolic profile including magnesium and other electrolytes (sodium, potassium, chloride, bicarbonate and magnesium), serum creatinine and serum glucose, coagulation panel: prothrombin time test (PTT) and international normalized ratio (INR), BUN, LFT panel: alanine transaminase (ALT), aspartate aminotransferase (AST) and bilirubin. All blood assessments will be done by the local laboratory. Results from local standard of care procedures and testing may be used. A central lab will not be used. Due to the short time-period from arrival at the hospital to the EVT, the results of the baseline blood work and the results from the initial ECG and CXR are not required prior to randomization or start of infusion. Baseline results from the primary hospital (within 8 hours) are accepted, if written documentation is available. Clinically significant laboratory findings that follow the initiation of the infusion (post dose) will be reported as AEs.

A baseline ECG and CXR will be obtained within 4 hours of admission and will represent the baseline measure of cardiopulmonary function. A repeat ECG and CXR will be obtained at 24h (+/- 4 hours), 48h (+/- 4 hours) and any new abnormality will be reported as an AE.

For elevated QTcF values, the patient is not to be automatically withdrawn from the study and the infusion will not be automatically stopped. Determination of continuation in the study will be at the clinical judgment of the investigator and/or the medical monitor as detailed in the instructions

on repeating ECGs below. Cardiologist consultation should be used to correct and/or overread an ECG with elevated QTcF values.

For Day 1 or Day 2 ECG:

If a subject has a QTcF > 500 ms with at least an increase from baseline > 40 ms, or an isolated increase from baseline > 70 ms, then the ECG must be repeated in approximately one hour and the ECGs must be over-read by a cardiologist. If a QTcF > 500 ms or an increase > 70 ms is confirmed and not due to a new bundle branch block (QRS > 110 ms), then the medical monitor must be contacted, and the following steps must be completed:

- 1) Study drug dosing must be stopped while serum electrolytes are evaluated, and it is determined if new medications that prolong the QTc interval were inadvertently initiated.
- 2) If no significant hypokalemia or hypomagnesemia are identified and no new medications that prolong the QTc interval were initiated, study drug must be discontinued, not to be restarted.
- 3) If significant hypokalemia or hypomagnesemia are identified, these must be corrected and if a new QT-prolonging medication was initiated, then the study drug must be stopped.
 - Study drug can be restarted after the QTcF is < 480 ms and the increase from baseline < 60 ms. ECGs must be repeated at approximately 2 hours and 6 hours post resumption of the dose and on the succeeding days of dosing.
- 4) If a repeat on-drug ECG's absolute QTcF > 500 ms or an increase from baseline > 70 ms is confirmed, study drug must be discontinued, not to be restarted.

If the initial increased QTcF occurs in the setting of a new bundle branch block, calculate the “adjusted QTcF” (See [Appendix 7: Adjusted QTcF Calculation](#)) and contact the Medical Monitor to discuss the management plan. If the Adjusted QTcF is < 500 ms and the increase from baseline is < 70 ms, drug infusion need not be stopped while contacting the Medical Monitor. Note: The adjusted QTcF calculation should be done by someone qualified and experienced in making this calculation.

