9.3.3 Analyses of Safety and Efficacy

All efficacy results will be examined using both ITT and per protocol populations. Although the trial's main purpose is to demonstrate safety, several measures of efficacy will be examined in order to provide effect size estimates for a appropriately powered future trial demonstrating efficacy. As such, both pairwise comparisons at various timepoints and longitudinal data will be examined.

- 1) Primary efficacy outcome
- 2) Secondary efficacy outcomes, as specified in the order presented below

Outcome	Statistical Analysis Methods
Primary	All analyses will be accomplished using SAS Software 9.4 (SAS Inc. Cary, NC). Primary: The frequency of SAEs, SAEs resulting in death, AEs, and discontinuations due to AEs will be summarized as counts and percentages between conditions. Comparisons will be conducted using Fisher's Exact tests.
Secondary	
Secondary: Comparisons between conditions for mRS will be evaluated using generalized mixed modeling assuming a binomial distribution (0-6) with sandwich estimation nested by site and participant, when applicable. Pairwise comparisons of mRS will be conducted at day 90 using a Dunnett correction. In addition, simple and interaction effects between pre-stroke, discharge, 30 and 90-day mRS by condition will be examined. Because superiority over placebo and lower dose is hypothesized, testing will reflect this superiority framework with one-tailed tests.
 
Both NIHSS score and BI at Day 90 will be examined in a similar fashion assuming a binomial distribution (0-42 & 0-100) with sandwich estimation nested by site and participant (when applicable). Pairwise comparisons between conditions will be conducted at day 90 using a Dunnett correction. In addition, simple and interaction effects between pre-treatment, discharge, 30 and 90-day NIHSS scores and BI by condition will be examined. Because superiority over placebo and lower dose is hypothesized, testing will reflect this superiority framework with one-tailed tests.
 
Mortality will be examined using Kaplan-Meier estimation with pairwise comparisons with a Dunnett correction with censoring on last known follow up. Because superiority over placebo and lower dose is hypothesized, testing will reflect this superiority framework with one-tailed tests. Marginal Cox Hazard regression will also be used to evaluate mortality with sandwich estimation and nesting within site.

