
Adverse Drug Reaction (ADR)
 
In the pre-approval clinical experience with a new medicinal product or its new usages, particularly as the therapeutic dose(s) may not be established: all noxious and unintended responses to a medicinal product related to any dose should be considered adverse drug reactions. The phrase "responses to a medicinal product" means that a causal relationship between a medicinal product and an adverse event is at least a reasonable possibility, i.e., the relationship cannot be ruled out.

Unexpected Adverse Drug Reaction
 
An adverse reaction, the nature or severity of which is not consistent with the applicable product information (e.g., Investigator's Brochure for an unapproved investigational medicinal product).

Events Meeting the AE Definition

• A new illness• The worsening of a concomitant illness• Any abnormal laboratory test results (hematology, clinical chemistry, or urinalysis) or other safety assessments (e.g., ECG, radiological scans, vital signs measurements), including those that worsen from baseline, considered clinically significant in the medical and scientific judgment of the investigator (i.e., not related to progression of underlying disease).• Exacerbation of a chronic or intermittent pre-existing condition including either an increase in frequency and/or intensity of the condition.• New conditions detected or diagnosed after study intervention administration even though it may have been present before the start of the study.• Signs, symptoms, or the clinical sequelae of a suspected drug-drug interaction.• Signs, symptoms, or the clinical sequelae of a suspected overdose of either study intervention or a concomitant medication. Overdose per se will not be reported as an AE/SAE unless it is an intentional overdose taken with possible suicidal/self-harming intent. Such overdoses should be reported regardless of sequelae.
Events NOT Meeting the AE Definition

- Any clinically significant abnormal laboratory findings or other abnormal safety assessments which are associated with the underlying disease.
- The disease/disorder being studied or expected progression, signs, or symptoms of the disease/disorder being studied, unless more severe than expected for the participant's condition.
- Medical or surgical procedure (e.g., endoscopy, appendectomy): the condition that leads to the procedure is the AE.

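### Protocol 8.1.2 and Appendix 4 set different AE thresholds for new ECG and chest X-ray findings, so AE counts depend on the rule a site follows and the any-AE comparison may be diluted or distorted

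*Protocol*

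**What the plan says.** Protocol 8.1.2 schedules a repeat ECG and chest X-ray at 24 h and 48 h and says of them that "any new abnormality will be reported as an AE". No clinical-significance or disease-related condition is attached.

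Protocol Appendix 4 (10.3) lists among events meeting the AE definition abnormal laboratory results or "other safety assessments (e.g., ECG, radiological scans, vital signs measurements", provided that they are "considered clinically significant in the medical and scientific judgment of the investigator". Its list of events that do not meet the definition begins with "Any clinically significant abnormal laboratory findings or other abnormal safety assessments which are associated with the underlying disease". Protocol 8.2 sends the reader to Appendix 4 for the AE definition.

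The neighbouring assessments use the Appendix 4 threshold. For laboratory results, 8.1.2 says "Clinically significant laboratory findings that follow the initiation of the infusion (post dose) will be reported as AEs". For vital signs, 8.1.1 says "Clinically significant findings post-dose will be reported as AEs".

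On analysis, the primary row of Protocol 9.3.3 states that "The frequency of SAEs, SAEs resulting in death, AEs, and discontinuations due to AEs will be summarized as counts and percentages between conditions", with comparison by Fisher's exact test. SAP 3.5.1 repeats only the general AE definition. It presents counts and percentages overall and by system organ class and preferred term, and names no test for AEs.

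**The concern.** A new non-specific ECG change, or a minor new opacity on the chest film, is an AE under 8.1.2 but not under Appendix 4 if the investigator judges it not clinically significant. A clinically significant ECG change attributed to the stroke is also an AE under the first rule and is expressly excluded by the second. A site cannot follow both rules.

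The exposure is wide, because the schedule of activities calls for both tests on Day 1 and Day 2 in every randomized participant. It also touches the main named hazard: Protocol 2.3.1 gives fluid volume overload as the major possible risk, and Table 10-1 gives monitoring of fluid as the purpose of the chest X-ray. At stake are the proportion of patients with any AE or TEAE, the event counts, and any comparison of these between arms.

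**Working it through.** **1. The two rules side by side**

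| Point | 8.1.2 | Appendix 4 |
|---|---|---|
| Tests covered | 24 h and 48 h ECG and CXR | Safety assessments, naming ECG and radiological scans |
| Clinical significance needed | No | Yes, in the investigator's judgment |
| Findings associated with the stroke | Counted | Not counted |

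Nothing in 8.1.2 says it overrides Appendix 4, and nothing in Appendix 4 makes an exception for 8.1.2. SAP 3.5.1 does not settle the matter.

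**2. Inputs for an illustration**

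The documents state no AE rate and no power calculation, so there is no figure of the plan's to reproduce.

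- From the Protocol: target of 100 participants, allocation 1:1:1 (4.1), so 100/3, about 33 per arm; alpha 0.05 (9.3.3).
- Assumed: two-sided Fisher test, since 9.3.3 does not state sidedness for AEs; AE proportions under Appendix 4 of p0 = 40% and p1 = 75% in the two arms compared; and q, the probability that a patient has a new ECG or CXR finding that counts only under 8.1.2, independent of other AEs.

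**3. Formulas**

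Under the 8.1.2 rule each proportion becomes p' = p + (1 − p)q. If q is the same in both arms, the difference becomes (p1 − p0)(1 − q). Power is exact, by enumerating both binomial distributions with n = 33.

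**4. Results**

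| q, lower-rate arm | q, higher-rate arm | Proportions with any AE | Difference (points) | Power |
|---|---|---|---|---|
| 0 | 0 | 40% / 75% | 35 | 79% |
| 0.2 | 0.2 | 52% / 80% | 28 | 59% |
| 0.3 | 0.3 | 58% / 82.5% | 24.5 | 49% |
| 0.5 | 0.5 | 70% / 87.5% | 17.5 | 31% |
| 0.2 | 0.4 | 52% / 85% | 33 | 77% |
| 0.1 | 0.3 | 46% / 82.5% | 36.5 | 84% |

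For example, with q = 0.3 in both arms: 0.40 + 0.60 × 0.3 = 0.58 and 0.75 + 0.25 × 0.3 = 0.825. With q = 0.1 and 0.3: 0.40 + 0.60 × 0.1 = 0.46 and 0.75 + 0.25 × 0.3 = 0.825.

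The difference grows rather than shrinks once the ratio of the two q values exceeds (1 − p0)/(1 − p1) = 0.60/0.25 = 2.4.

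**5. Other starting rates**

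From 30% and 60%, power is 64.6%. It falls to 34.6% if every site uses the 8.1.2 rule with q = 0.3 in both arms. It falls to 49.6% if half the caseload follows each rule (average q = 0.15, giving 40.5% and 66%).

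**6. Direction by contrast**

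Placebo and the high dose are planned at the same infusion rate, and the low dose at half that rate (Protocol Table 6-1). If new chest-film findings track volume, their frequency should be similar for high dose and placebo, which favours dilution. They would be less frequent on low dose than on placebo, and counting all of them could then create or widen an apparent difference in favour of the low dose.

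**The case against.** The strongest reply is that 8.1.2 may be a deliberate, more inclusive rule for two cardiopulmonary tests in a safety trial, and that little depends on it. Much of this stands.

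- AEs are listed in the synopsis as an additional safety outcome. Protocol 9.3.2 makes SAEs and 90-day mortality the main analyses, and an asymptomatic ECG or CXR change would rarely meet a seriousness criterion.
- Each site has its own randomization table (Protocol 6.3), so a site's rule applies to all its arms. Mixed practice adds between-site variation rather than direct bias between arms.
- The SAP supersedes the protocol where they differ (SAP 1) and names no AE test, so it is unclear whether the Fisher comparison of AEs is still planned.

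A reader might infer that the AE comparison is necessarily diluted, or that a real difference in fluid-related AEs would be hidden. The documents do not support either. Dilution follows if the extra findings are equally frequent across arms, and no rates are given; the table above shows that it can also go the other way. The calculation concerns the any-AE proportion only. SAP 3.5.1 tabulates by preferred term, so an incidental ECG change does not alter the count for a fluid-overload term, and SAP 3.5.4 reports QTcF categories by arm.

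What does not stand is that the text can be left alone. No sentence marks 8.1.2 as an intended exception, and the general definition that 8.2 points to says otherwise for the same tests.

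**Conclusion.** The contradiction is real, lies in current protocol text, and is not resolved by the SAP. AE and TEAE counts depend on which rule a site applies, and the any-AE comparison may be diluted or distorted. The main SAE and mortality endpoints are largely untouched.

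The size is illustrative only. With 33 per arm and assumed rates of 40% and 75%, power moves from 79% to between 59% and 31% when incidental findings occur equally in 20% to 50% of patients. It moves to 84% when they occur in 10% and 30%. All of these rates are assumptions, as is the two-sided test.

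A reader might also infer that adopting the narrower rule loses nothing. That does not hold for the chest X-ray: SAP 3.5.6 only lists CXR results with flags, so findings below the significance threshold would drop out of every by-arm table.

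**What to change.** Reconcile 8.1.2 and Appendix 4 to one stated AE-reporting rule for new ECG and CXR findings, and repeat it in SAP 3.5.1 and the CRF guidance. Record every new ECG or CXR abnormality with a clinical-significance flag. Tabulate by arm both all new abnormalities and those meeting the Appendix 4 definition, so that subclinical fluid findings on the chest film stay in the by-arm comparison whichever rule is chosen. In the same edit, state in the SAP whether Fisher tests on AEs are still planned.

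The cost is one protocol sentence, one CRF flag and one extra table, plus the matching lines in the SAP and CRF guidance.
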